4.4.2.10. Neurologic Disorders

Myasthenia gravis and Guillain-Barré syndrome have been observed with single-agent atezolizumab. Patients may present with signs and symptoms of sensory and/or motor neuropathy. Diagnostic workup is essential for an accurate characterization to differentiate between alternative etiologies. Management guidelines for neurologic disorders are provided in [Table 12](#).

Table 12: Management Guidelines for Neurologic Disorders

Event	NCI CTCAE Grade	Recommended Medical Management
Immune-mediated neuropathy	Grade 1	
 Continue atezolizumab. Investigate etiology.
	Grade 2	
 Withhold atezolizumab for up to 12 weeks after event onset.^a Investigate etiology. Initiate treatment as per institutional guidelines. If event resolves to Grade 1 or better, resume atezolizumab.^b If event does not resolve to Grade 1 or better while withholding atezolizumab, permanently discontinue atezolizumab and contact Medical Monitor(s).
	Grade 3 or higher	
 Permanently discontinue atezolizumab and contact Medical Monitor(s). Initiate treatment as per institutional guidelines.
Myasthenia gravis and Guillain-Barré syndrome	Any grade	
 Permanently discontinue atezolizumab and contact Medical Monitor(s). Refer patient to neurologist. Initiate treatment as per institutional guidelines. Consider initiation of corticosteroids equivalent to 1–2 mg/kg/day oral or IV prednisone.

Abbreviations: CTCAE = Common Terminology Criteria for Adverse Events; IV = intravenous; NCI = National Cancer Institute

^a Atezolizumab may be withheld for a longer period of time (i.e., > 12 weeks after event onset) to allow for corticosteroids (if initiated) to be reduced to the equivalent of ≤ 10 mg/day oral prednisone. The acceptable length of the extended period of time must be agreed upon by the Investigator and the Medical Monitor(s).

^b If corticosteroids have been initiated, they must be tapered over ≥ 1 month to the equivalent of ≤ 10 mg/day oral prednisone before atezolizumab can be resumed.

4.4.2.11. Immune-mediated Meningoencephalitis

Immune-mediated meningoencephalitis is an identified risk associated with the administration of atezolizumab. Immune-mediated meningoencephalitis should be suspected in any patient presenting with signs or symptoms suggestive of meningitis or encephalitis, including, but not limited to, headache, neck pain, confusion, seizure, motor or sensory dysfunction, and altered or depressed level of consciousness. Encephalopathy from metabolic or electrolyte imbalances needs to be distinguished from potential meningoencephalitis resulting from infection (bacterial, viral, or fungal) or progression of malignancy, or secondary to a paraneoplastic process.

All patients being considered for meningoencephalitis should be urgently evaluated with a CT scan and/or MRI scan of the brain to evaluate for metastasis, inflammation, or edema. If deemed safe by the treating physician, a lumbar puncture should be performed and a neurologist should be consulted.

Patients with signs and symptoms of meningoencephalitis, in the absence of an identified alternate etiology, should be treated according to the guidelines in [Table 13](#).

Table 13: Management Guidelines for Immune-mediated Meningoencephalitis

Event	NCI CTCAE Grade	Recommended Medical Management
Immune-mediated meningoencephalitis	All grades	
 • Permanently discontinue atezolizumab and contact Medical Monitor(s). • Refer patient to neurologist. • Initiate treatment with corticosteroids equivalent to 1–2 mg/kg/day IV methylprednisolone and convert to 1–2 mg/kg/day oral prednisone or equivalent upon improvement. • If event does not improve within 48 hours after initiating corticosteroids, consider adding an immunosuppressive agent. • If event resolves to Grade 1 or better, taper corticosteroids over ≥ 1 month.

Abbreviations: CTCAE = Common Terminology Criteria for Adverse Events; IV = intravenous; NCI = National Cancer Institute

4.4.2.12. Renal Events

Immune-mediated nephritis has been associated with the administration of atezolizumab. Eligible patients must have adequate renal function, and renal function, including serum creatinine, should be monitored throughout study treatment. Patients with abnormal renal function should be evaluated and treated for other more common etiologies (including prerenal and postrenal causes, and concomitant medications such as nonsteroidal anti-inflammatory drugs). Refer the patient to a renal specialist if clinically indicated. A renal biopsy may be required to enable a definitive diagnosis and appropriate treatment.

Patients with signs and symptoms of nephritis, in the absence of an identified alternate etiology, should be treated according to the guidelines in [Table 14](#).

Table 14: Management Guidelines for Renal Events

Event	NCI CTCAE Grade	Recommended Medical Management
Renal event	Grade 1	
 Continue atezolizumab. Monitor kidney function, including creatinine, closely until values resolve to within normal limits or to baseline values.
	Grade 2	
 Withhold atezolizumab for up to 12 weeks after event onset.^a Refer patient to renal specialist. Initiate treatment with corticosteroids equivalent to 1–2 mg/kg/day oral prednisone. If event resolves to Grade 1 or better, resume atezolizumab.^b If event does not resolve to Grade 1 or better while withholding atezolizumab, permanently discontinue atezolizumab and contact Medical Monitor(s).
	Grade 3 or higher	
 Permanently discontinue atezolizumab and contact Medical Monitor(s). Refer patient to renal specialist and consider renal biopsy. Initiate treatment with corticosteroids equivalent to 1–2 mg/kg/day oral prednisone. If event does not improve within 48 hours after initiating corticosteroids, consider adding an immunosuppressive agent. If event resolves to Grade 1 or better, taper corticosteroids over \geq 1 month.

Abbreviations: CTCAE = Common Terminology Criteria for Adverse Events; NCI = National Cancer Institute

^a Atezolizumab may be withheld for a longer period of time (i.e., $>$ 12 weeks after event onset) to allow for corticosteroids (if initiated) to be reduced to the equivalent of \leq 10 mg/day oral prednisone. The acceptable length of the extended period of time must be agreed upon by the Investigator and the Medical Monitor(s).

^b If corticosteroids have been initiated, they must be tapered over \geq 1 month to the equivalent of \leq 10 mg/day oral prednisone before atezolizumab can be resumed.

4.4.2.13. Immune-mediated Myositis

Immune-mediated myositis has been associated with the administration of atezolizumab. Myositis or inflammatory myopathies are a group of disorders sharing the common feature of inflammatory muscle injury; dermatomyositis and polymyositis are among the most common disorders. Initial diagnosis is based on clinical (muscle weakness, muscle pain, skin rash in dermatomyositis), biochemical (serum creatine kinase increase), and imaging (electromyography/MRI) features, and is confirmed with a muscle biopsy.

Patients with signs and symptoms of myositis, in the absence of an identified alternate etiology, should be treated according to the guidelines in [Table 15](#).

Table 15: Management Guidelines for Immune-mediated Myositis

Event	NCI CTCAE Grade	Recommended Medical Management
Immune-mediated myositis	Grade 1	
 Continue atezolizumab. Refer patient to rheumatologist or neurologist. Initiate treatment as per institutional guidelines.
	Grade 2	
 Withhold atezolizumab for up to 12 weeks after event onset^a and contact Medical Monitor(s). Refer patient to rheumatologist or neurologist. Initiate treatment as per institutional guidelines. Consider treatment with corticosteroids equivalent to 1–2 mg/kg/day IV methylprednisolone and convert to 1–2 mg/kg/day oral prednisone or equivalent upon improvement. If corticosteroids are initiated and event does not improve within 48 hours after initiating corticosteroids, consider adding an immunosuppressive agent. If event resolves to Grade 1 or better, resume atezolizumab.^b If event does not resolve to Grade 1 or better while withholding atezolizumab, permanently discontinue atezolizumab and contact Medical Monitor(s).
	Grade 3	
 Withhold atezolizumab for up to 12 weeks after event onset^a and contact Medical Monitor(s). Refer patient to rheumatologist or neurologist. Initiate treatment as per institutional guidelines. Respiratory support may be required in more severe cases. Initiate treatment with corticosteroids equivalent to 1–2 mg/kg/day IV methylprednisolone, or higher-dose bolus if patient is severely compromised (e.g., cardiac or respiratory symptoms, dysphagia, or weakness that severely limits mobility); convert to 1–2 mg/kg/day oral prednisone or equivalent upon improvement. If event does not improve within 48 hours after initiating corticosteroids, consider adding an immunosuppressive agent. If event resolves to Grade 1 or better, resume atezolizumab.^b If event does not resolve to Grade 1 or better while withholding atezolizumab, permanently discontinue atezolizumab and contact Medical Monitor(s). For recurrent events, treat as a Grade 4 event.

Event	NCI CTCAE Grade	Recommended Medical Management
Immune-mediated myositis	Grade 4	
 • Permanently discontinue atezolizumab and contact Medical Monitor(s). • Refer patient to rheumatologist or neurologist. • Initiate treatment as per institutional guidelines. Respiratory support may be required in more severe cases. • Initiate treatment with corticosteroids equivalent to 1–2 mg/kg/day IV methylprednisolone, or higher-dose bolus if patient is severely compromised (e.g., cardiac or respiratory symptoms, dysphagia, or weakness that severely limits mobility); convert to 1–2 mg/kg/day oral prednisone or equivalent upon improvement. • If event does not improve within 48 hours after initiating corticosteroids, consider adding an immunosuppressive agent. • If event resolves to Grade 1 or better, taper corticosteroids over ≥ 1 month.

Abbreviations: CTCAE = Common Terminology Criteria for Adverse Events; IV = intravenous; NCI = National Cancer Institute

- ^a Atezolizumab may be withheld for a longer period of time (i.e., > 12 weeks after event onset) to allow for corticosteroids (if initiated) to be reduced to the equivalent of ≤ 10 mg/day oral prednisone. The acceptable length of the extended period of time must be agreed upon by the Investigator and the Medical Monitor(s).
- ^b If corticosteroids have been initiated, they must be tapered over ≥ 1 month to the equivalent of ≤ 10 mg/day oral prednisone before atezolizumab can be resumed.

4.4.2.14. Systemic Immune Activation

Systemic immune activation is a rare condition characterized by an excessive immune response. Given the mechanism of action of atezolizumab, systemic immune activation is considered a potential risk for atezolizumab.

Recommendations regarding early identification and management of systemic immune activation are provided below. In the event of suspected systemic immune activation, atezolizumab should be withheld and clinical specialists (e.g., rheumatology, clinical immunology, or solid organ or hematopoietic stem cell transplant specialists) and the Medical Monitor(s) should be informed.

Early disease recognition is critical, and systemic immune activation should be suspected if, in the absence of an alternative etiology, the patient meets two or more of the following criteria:

- Hypotension that is refractory to aggressive IV fluid challenge (vasopressor support may be required).
- Respiratory distress that requires aggressive supportive care (supplemental oxygen and intubation may be required).
- Fever $> 38.5^{\circ}\text{C}$
- Acute renal or hepatic failure
- Bleeding from coagulopathy
- Any of the following unexplained laboratory abnormalities (change from baseline): cytopenias (in two or more lineages), significant transaminitis, or coagulopathy

For patients with suspected systemic immune activation, an initial evaluation should include the following:

- Complete blood count with peripheral smear
- Prothrombin time (PT), activated partial thromboplastin time (aPTT), fibrinogen, and D-dimer
- Ferritin
- Soluble IL-2 receptor (soluble CD25)
- Triglycerides
- Aspartate aminotransferase (AST), alanine aminotransferase (ALT), and direct bilirubin
- Lactate dehydrogenase (LDH)
- Complete neurologic and abdominal examination (assess for hepatosplenomegaly)

Laboratory tests with normal results should be repeated frequently in patients for whom a high clinical suspicion of systemic immune activation exists.

If neurologic abnormalities are present, consider cerebrospinal fluid analysis and/or an MRI of the brain.

If cytopenias are present (Grade ≥ 2 in two or more lineages) or ferritin is ≥ 3000 ng/mL, the following evaluations should also be performed:

- Bone marrow biopsy and aspirate (assess for evidence of hemophagocytosis)
- Adenovirus, cytomegalovirus, Epstein Barr virus, herpes simplex virus, and human herpes virus 6, 7, and 8 evaluation (for reactivated or active disease)

Diagnostic criteria and recommended management for systemic immune activation are provided in [Table 16](#). The diagnostic criteria apply only when alternative etiologies have been excluded.

An AE of systemic immune activation should be reported on the Adverse Event electronic case report form (eCRF) if the event meets the criteria for “consistent with systemic immune activation” or “probable systemic immune activation” as outlined in [Table 16](#).

Table 16: Systemic Immune Activation Diagnosis and Management

Systemic Immune Activation Diagnostic Criteria (Applicable Only When Alternative Etiologies are Excluded)		
Major Criteria		Minor Criteria

 • Fever $\geq 38.5^{\circ}\text{C}$ on more than one occasion • Ferritin $\geq 3000 \text{ ng/mL}$ • Cytopenias (Grade ≥ 2 in two or more lineages) • Age-adjusted soluble interleukin-2 receptor elevated by ≥ 2 standard deviations • Severe (Grade ≥ 3) or progressive dysfunction in two or more organs • Decreased fibrinogen 		
 • Splenomegaly • Hemophagocytosis in bone marrow, spleen, or lymph nodes • Elevated gamma-glutamyl transpeptidase or liver function tests (aspartate aminotransferase, alanine aminotransferase, or direct bilirubin) • Elevated triglycerides • Elevated lactate dehydrogenase • Decreased natural killer cell activity
Diagnosis and Management of Systemic Immune Activation		
Number of Criteria	Diagnosis	Action to Be Taken
≥ 4 major criteria	Consistent with systemic immune activation	
 • Permanently discontinue atezolizumab. • Consider treatment with an immunosuppressive agent (i.e., cytokine inhibitors) and intravenous corticosteroids (i.e., methylprednisolone 1 g once daily or equivalent, or dexamethasone $\geq 10 \text{ mg/m}^2$ once daily if neurologic abnormalities are present). • Inform the Medical Monitor(s). • Consider HLH-2004 protocol (Henter et al 2007) if there is no clinical improvement.

3 major criteria OR 2 major plus ≥ 3 minor criteria	Probable systemic immune activation	
 Depending on clinical severity, follow guidelines for “Consistent with systemic immune activation” or “Possible systemic immune activation” diagnosis. Clinical specialists may be contacted for recommendations and the Medical Monitor(s) should be informed.
2 major plus ≤ 2 minor criteria OR 1 major plus ≥ 4 minor criteria	Possible systemic immune activation	
 Withhold atezolizumab. Consider treatment with intravenous corticosteroids. Clinical specialists may be contacted for additional recommendations and the Medical Monitor(s) should be informed. Follow guidelines for “Consistent with systemic immune activation” diagnosis if there is no clinical improvement or if clinical worsening occurs. If clinical improvement occurs, atezolizumab may be resumed following a benefit-risk assessment by the Medical Monitor(s).

Notes: Criteria are adapted from a Delphi Survey of 26 experts who provided helpful criteria in the positive diagnosis of hemophagocytic syndrome in adult patients ([Hejblum et al 2014](#)).

Grades are based on National Cancer Institute Common Terminology Criteria for Adverse Events.

These recommendations do not replace clinical judgment and are intended as suggested guidance.

4.5. Stopping Rules

The Sponsor may stop this study at any time. Investigators will be notified by the Sponsor or its designee if the study is stopped. The occurrence of the following events will require that further enrollment in the study be stopped:

- Grade 3 or higher systemic infection assessed as definitely related to SYNB1891.
- Death assessed as at least possibly related to study treatment.
- The Investigator, Medical Monitor(s), and/or Sponsor determines that an event or current data warrant stopping the study.

The SRC will review the data concerning these event(s), along with all other available data. Based on the results of their investigation, the SRC will determine appropriate follow-up and decide whether the study should be continued, amended or stopped.

If the study is stopped, the events will be investigated, and the study will be closed to further enrollment. Patients already participating in the study at the time the study is stopped will not receive further study treatment and the evaluations for the End-of-treatment (EOT)/Early Termination visit will be performed.

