4.3. Intrapatient Dose Modification

Every effort should be made to administer study treatment on the planned dose and schedule.

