4.3.1. Dosing Delays and Interruptions

Study treatment dosing delays will be permitted in any treatment cycle if unforeseen circumstances prevent the patient from returning to the clinic on the scheduled day(s). A maximum delay of 2 days in Cycle 1 will be permitted. If administration of study treatment is delayed by > 2 days in Cycle 1, that dose is considered missed and the patient should receive the next dose at the next visit.

If a patient misses ≥ 2 SYNB1891 doses in Cycle 1, then the patient will be discontinued permanently from treatment and may be replaced (see Section 8.2.1). In Cycle 2 and beyond, if a patient misses the dose of SYNB1891, then the patient may be discontinued permanently from treatment, unless the Investigator's assessment of the benefit/risk suggests otherwise (after consultation with Sponsor). If treatment is permanently discontinued, patients will continue to be followed for safety as indicated for end of treatment and follow-up.

SYNB1891 treatment interruption can occur due to treatment-related toxicity, including Grade 3 or higher infections or local inflammation requiring antibiotics, and the start of a new cycle may not occur until the following criteria have been met:

- Nonhematologic toxicities have returned to either baseline or Grade ≤ 1 , or at the Investigator's discretion, Grade ≤ 2 if not considered a safety risk. This condition must be met within 14 days of the initial treatment interruption.
- Hematologic toxicities: ANC $\geq 1000/\text{mm}^3$ or have returned to baseline levels; platelet count $\geq 50,000/\text{mm}^3$ or has returned to baseline levels. This condition must be met within 14 days of the initial treatment interruption.
- If a patient requires treatment with a systemic antibiotic on study, SYNB1891 should be held for the duration of the antibiotic regimen and for 5 half-lives after the last dose of antibiotics. Once the patient is apyretic after completion of the antibiotic washout period, SYNB1891 may resume.

If the patient cannot meet the above conditions within the specified time frame, then study treatment should be permanently discontinued, unless the Investigator's assessment of the benefit/risk suggests otherwise (after consultation with Sponsor). The patient may be replaced (see Section 8.2.1).

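### At a stopping-rule event, Section 4.5 expressly stops only enrollment: it states no interim dosing hold or review time, and it is unclear when treatment of current patients ends

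*Protocol*

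**What the plan says.** Protocol Section 4.5 names three triggers: a Grade 3 or higher systemic infection definitely related to SYNB1891; a death at least possibly related to study treatment; and a judgment by the Investigator, Medical Monitor or Sponsor that stopping is warranted. The stated consequence is: "The occurrence of the following events will require that further enrollment in the study be stopped". The SRC then reviews the data and must "decide whether the study should be continued, amended or stopped". No time is given for this. Section 9.7 schedules the SRC only when a cohort has completed Cycle 1.

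The last paragraph of Section 4.5 reads: "If the study is stopped, the events will be investigated, and the study will be closed to further enrollment". It continues: "Patients already participating in the study at the time the study is stopped will not receive further study treatment".

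Other sections bear on dosing in the meantime:

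- Section 4.3: "Every effort should be made to administer study treatment on the planned dose and schedule".
- Section 4.3.1: "dosing delays will be permitted in any treatment cycle if unforeseen circumstances prevent the patient from returning to the clinic", and "SYNB1891 treatment interruption can occur due to treatment-related toxicity", with restart tied to that patient's own recovery. For timing: "A maximum delay of 2 days in Cycle 1 will be permitted". A later dose counts as missed, and two missed Cycle 1 doses mean permanent discontinuation. Atezolizumab may be suspended for reasons other than toxicity if the Medical Monitor approves.
- Section 4.2.1: the additional cycles, 5 to 35, run only until a predefined stopping rule is met. The text for Cycles 1 to 4 has no such clause.
- Sections 4.2.2 and 4.2.3: the other patients in a cohort are not dosed until the Sentinel patient's data have been reviewed on or after Day 7. Section 4.2.2 also bars further injections for the Sentinel until then, stated for Arm 1.

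The SAP adds no stopping procedure. Its Appendix 3 footnotes repeat the stopping-rule clause for additional cycles.

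**The concern.** The two specified triggers are the most serious events the protocol foresees for a first-in-human live bacterial product. When one occurs, sites need to know the same day whether to give the next injection to everyone else. Section 4.5 answers for patients not yet enrolled and leaves the rest to the reader's view of *stopped*. Two sites could act differently after the same death.

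Both courses carry a cost. If dosing continues, other patients are injected at the same or a higher dose while the event is unexplained. Section 4.2.3 keeps Arm 2 at least one level below the dose being evaluated in Arm 1, so an Arm 2 event can occur while Arm 1 patients receive more SYNB1891. If a site improvises a hold, Section 4.3.1 penalises the patient through the missed-dose rule, and the DLT data that drive escalation may be lost. Those patients can be replaced, but not while the trigger keeps enrollment closed.

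**Working it through.** The plan gives no figure to reproduce, so the check is a comparison of text followed by a dosing-calendar count.

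**1. What *stopped* means**

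- *It means the trigger.* The last paragraph of Section 4.5 attaches investigation and closed enrollment to the study being stopped, and both already follow a trigger. The third trigger is itself a judgment that stopping is warranted. On this reading treatment ends at once.
- *It means the SRC's decision.* The SRC may choose to continue, which makes little sense if the study has already been stopped and everyone taken off treatment. On this reading dosing goes on during the review.

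The second reading is the more literal, but the text does not settle it.

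**2. Whether other text fills the gap**

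- Cycles 5 to 35: yes, Section 4.2.1 read literally ends treatment at the trigger.
- Cycles 1 to 4: no. The grounds for delay or interruption in Section 4.3.1 concern the patient's own circumstances or toxicity, and the antibiotic hold in Table 2 covers only the patient being treated.
- Enrolled but undosed patients: no. Section 7.1 allows up to 5 calendar days between enrollment and first dose, so stopping enrollment does not by its terms stop that dose.
- SAE reporting within 24 hours (Section 9.4) and Medical Monitor review (Section 9.7) are neither a hold nor an SRC deadline.

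**3. Injections due if there is no hold**

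Inputs: Days 1, 8 and 15 of Cycle 1, then Day 1 of each 21-day cycle (Section 4.2.1), so Cycle 2 Day 1 is Day 22. Review length is an assumption.

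- A patient who has just had Day 1 is due 1 injection in 7 days (Day 8), 2 in 14 days (Days 8, 15) and 3 in 21 days (Days 8, 15, 22). In Arm 2 the 21-day case adds one atezolizumab infusion.
- Other patients at one dose level, for a cohort of 3 to 6 (Section 4.2.3): 3 − 1 = 2 to 6 − 1 = 5, so up to 2 to 5 injections per 7 days in such a cohort.

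**4. What a hold does under the current Section 4.3.1**

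A hold of L days starting on Day s bars dosing on Days s to s + L − 1, and dosing resumes on Day s + L. Counting the 2-day allowance from the nominal day, the last permitted days are 8 + 2 = Day 10 for dose 2 and 15 + 2 = Day 17 for dose 3.

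If dose 2 would have been given on Day d, both remaining Cycle 1 doses are missed when s ≤ d and s + L > 17. The shortest such hold is L = 18 − d:

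- d = 8: 18 − 8 = 10 days
- d = 9 (within the 1-day visit window): 18 − 9 = 9 days
- d = 10 (maximum delay): 18 − 10 = 8 days

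So 7 days is the longest hold at which no patient without an earlier missed dose misses two. For L = 7 and a patient on schedule:

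| Hold starts on Day | Effect | Start days |
|---|---|---|
| 2, 3, 9, 10 | Cycle 1 dose late, within 2 days | 4 |
| 4–8, 11–15 | One Cycle 1 dose missed | 10 |
| 16–21 | Cycle 2 Day 1 delayed by s + 7 − 22 = 1 to 6 days | 6 |

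These total 4 + 10 + 6 = 20 start days, none with two missed doses. The exception is a patient who had already missed dose 2 for another reason: a 7-day hold starting on Days 11–15 takes dose 3 as well.

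**The case against.** The strongest reply is that the protocol has more protection than Section 4.5 alone suggests. Section 4.2.1 ends the additional cycles when a stopping rule is met. The Sentinel gate means that an event in a Sentinel patient before the review exposes no one else in a new cohort. The SRC reviews Sentinel DLTs individually, so it does act outside its cohort-end meetings. Investigators, who sit on the SRC, may end a patient's dosing for medical reasons (Section 8.2), and the Sponsor may stop the study at any time.

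All of this stands and narrows the point. It does not close it. The Sentinel gate covers only the start of a cohort, the Section 4.2.1 clause misses the weekly-injection period, and the rest is discretion.

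Three stronger inferences should be resisted:

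- *The plan requires dosing to continue after a related death.* It does not. One of two readings of Section 4.5 ends treatment at the trigger, and the literal reading leaves room for discretion.
- *Two to five injections is the worst case.* It is neither a bound nor always reached. A dose level may hold up to 14 patients and the expansion up to 20 more, while behind the Sentinel gate the count can be zero.
- *Losing both concurrently dosed non-Sentinel patients would break a replacement limit.* One replacement per cohort is a planning allowance within a total of approximately 70, and Section 8.2.1 sets no cap.

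**Conclusion.** The point holds in limited form. Section 4.5 explicitly requires only that enrollment stop, does not make clear when treatment of current patients ends, and states neither an interim hold nor a review time. The exposed group is patients in Cycles 1 to 4, above all those on weekly injections, and those enrolled but not yet dosed. For Cycle 5 onward the difficulty is different: Section 4.2.1 appears to end treatment at the trigger, which is hard to square with an SRC that may decide to continue.

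The injection counts are illustrative. They assume a review length, a cohort of 3 to 6 with every other patient in Cycle 1, and no use of discretion. The 7-day result rests on the Section 4.3.1 rules, with delays counted from the nominal visit day. Confidence is medium because the reading of *stopped* is open. The wording should be corrected: the events are grave, the product is new to humans, and the change is cheap.

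**What to change.** 1. **Section 4.5, hold.** After a definitely related Grade 3 or higher systemic infection or an at least possibly related death, hold SYNB1891 for all patients in both arms, including those enrolled but not yet dosed. Hold atezolizumab in Arm 2 if the event is at least possibly related to it; Section 9.1.2 already requires separate causality assessments. The hold runs from Sponsor notification until the SRC decides. The SRC may release lower dose levels early. A hold limited to the implicated dose and above would leave Arm 2 combination patients on SYNB1891 after an event at the current Arm 1 dose.
2. **Section 4.5, timing.** The SRC meets ad hoc and decides within a stated time. Seven calendar days is a suggestion, chosen from the calendar result above.
3. **Meaning of *stopped*.** Define it as the SRC's or Sponsor's decision to stop the study. Change the stopping-rule clause in Section 4.2.1, the synopsis and the footnotes to Tables 19 and 20 to match, and the copies in SAP Appendix 3.
4. **Section 4.3.1.** Doses missed because of this hold do not count toward the missed-dose discontinuation rules. DLT evaluability stays as it is: a DLT, or 2 of 3 injections. Patients left non-evaluable may be replaced once enrollment reopens.

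The cost is wording in a protocol amendment, using the existing SRC and adding no visits. A held patient may lose one Cycle 1 injection or have a later dose delayed by up to about 7 days. A patient with an earlier missed dose may need replacement.
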